2.1 Hypotheses and Research Questions

2.1.1 MMF versus placebo

Hypothesis 1: Long-acting corticosteroid-induced improvement in lupus disease activity achieved prior to randomization will be lost more rapidly in the placebo arm compared to the MMF arm.

Research Question 1: Are there immunologically definable subsets of SLE patients [1] for whom MMF is an effective treatment?

Hypothesis 2: Expression of TWEAK, complement receptor 3 (CR3), FYN, IL16, IL17RA, and/or IL2RB will decline over 24 weeks for those participants on MMF who do not develop treatment failure compared to those who do fail on or prior to week 24.

2.1.2 MMF versus MMF plus Voclosporin

Research Question 2: Do baseline gene expression patterns characterizing response (or non-response) to MMF and MMF plus voclosporin differ?

2.2 Primary Objective

Assuming that MMF is an effective treatment in some, but not all, SLE patients, the primary objective of this study is to evaluate the potential effectiveness of 24 weeks of MMF within previously discovered immunologically defined subsets of SLE patients [1].

This objective will be most effectively supported within the context of a successful demonstration of superiority of MMF over placebo, pooled over all clusters. To this end, individuals with lupus who are without organ-threatening disease will be randomized to 24 weeks of MMF or placebo. The primary objective is to compare the cumulative incidence of treatment failure with 24 weeks of MMF or placebo by treatment arm. Subsequently, treatment effects will be evaluated within the individual immunologically-homogenous subsets defined at screening.

2.3 Secondary Objectives

- To describe the effects of long-acting corticosteroid injections, MMF, MMF plus voclosporin, and placebo on measures of safety and toxicity.
- To describe the effects of MMF, MMF plus voclosporin, and placebo on exploratory clinical response measures and disease flare indices.
- To describe the effects of MMF, MMF plus voclosporin, and placebo on patient-reported quality of life indices.

2.4 Mechanistic Objectives

- To explore and compare pre-randomization gene expression patterns among responders and non-responders to MMF and MMF plus voclosporin.
- To use comprehensive immunophenotyping to study the immunologic changes that accompany treatment-induced disease improvement to better understand key checkpoints in SLE pathophysiology.
- To use comprehensive immunophenotyping to better understand immunologic changes associated with the loss of clinical response.

3 Study Design

3.1 Description of Study Design

This will be a multicenter, double blind, placebo-controlled Phase 2 trial of 120 participants with SLE who will enter with significant symptoms, but no organ-threatening disease. The study will be conducted in 3 stages.

3.1.1 Stage 1: Treatment Withdrawal:

During Stage 1, which may last up to 4 weeks, consenting participants will receive an IM injection of a long-acting corticosteroid, which may be repeated if needed to achieve amelioration of symptoms. A total of 3 corticosteroid injections may be given during Stage 1 with the first injection given as early as the Screening Visit after the mechanistic blood draw is completed and the last injection given as late as the Stage 2 Randomization Visit after the mechanistic blood draw is completed. Dose will be dependent on the available formulation.

In addition, participants will withdraw from all other treatments for lupus with the following exceptions: (i) PRN nonsteroidal anti-inflammatory treatments may be started or continued, (ii) PRN topicals may be continued, (iii) hydroxychloroquine, chloroquine, or quinacrine may be continued at any stable dose, and (iv) prednisone, if ≤ 10 mg/day, may be continued at stable doses but not started. Participants may screen if taking up to 20 mg/day prednisone (or equivalent) but both the participant and the investigator must be willing and able to taper to 10 mg/day (under cover of long-acting corticosteroids) by the Stage 2 Randomization Visit. Withdrawal of background lupus medications can start any time after the first corticosteroid injection is given but must be completed by the Stage 2 Randomization Visit.

3.1.2 Stage 2: Randomization

One hundred and twenty qualifying participants who withdraw from treatment as described in protocol Section 3.1.1, *Stage 1: Treatment Withdrawal*, and meet improvement criteria for randomization as outlined in Section 4.2.2, *Inclusion criteria required prior to randomization*, will be randomized (1:1) to receive up to 48 weeks of either MMF or corresponding MMF placebo. For the first 2 weeks, a scheduled “taper-up” of MMF will take place. Participants will receive 500 mg MMF (or corresponding MMF placebo) BID for 7 days, followed by 500mg and 1,000mg MMF (or corresponding MMF placebo) in divided doses for 7 days. They will then continue at a stable dose of 1,000mg MMF (or corresponding MMF placebo) BID. Visits to evaluate AEs, vital signs, hematology and chemistry, study medication compliance, medication use, disease status, participant reported outcomes, and to obtain biomarker samples will occur every 4 weeks after randomization.

Participants will be followed for a maximum of 48 weeks on study-provided medication in Stage 2. If a participant experiences an increase in SLE symptoms at any scheduled or unscheduled visit at or before the Stage 2 Week 24 visit, they will proceed in the study as follows:

- If the participant is deemed a Stage 2 treatment failure as defined in protocol Section 3.2, *Primary Endpoint*, and a corticosteroid injection is deemed sufficient for treatment without new or increased lupus medication, then a blood sample for mechanistic studies will be drawn, the injection will be administered, and the participant will immediately proceed to Stage 3: Re-randomization. (See Section 3.1.3, *Stage 3 Re-Randomization*).
- If the participant is deemed a Stage 2 treatment failure as defined in protocol Section 3.2, *Primary Endpoint*, and a corticosteroid injection is deemed sufficient for treatment without new or increased lupus medication, but the participant refuses the corticosteroid injection, then a blood sample for mechanistic studies will be drawn, and the participant will still immediately proceed to Stage 3: Re-randomization without the corticosteroid injection. (See Section 3.1.3, *Stage 3: Re-Randomization*).
- If the participant is deemed a Stage 2 treatment failure as defined in protocol Section 3.2, *Primary Endpoint*, and a corticosteroid injection is deemed insufficient and a new or increased lupus medication is required, then a blood sample for mechanistic studies will be drawn, Stage 2 study-provided medication will be stopped, and the new or increased lupus medication will be started outside of the study. The participant will not be eligible for Stage 3 but will be followed to Stage 2 Week 24 or 4 weeks \pm 10 days after the last dose of study-provided medication, whichever is later, before exiting the study. Participants who exit the study at Stage 2 Week 24 should complete all End of Study/Safety Follow-Up visit assessments at this time.

Participants who have not failed Stage 2 on or before the Stage 2 Week 24 visit will continue on Stage 2 study-provided medication through Stage 2 Week 48 or until treatment failure, whichever occurs first.

- If the participant is deemed a Stage 2 treatment failure after Stage 2 Week 24, then study-provided medication will be stopped. Prior to treatment with a corticosteroid injection or a new or increased lupus medication outside of the study, a blood sample for mechanistic studies will be drawn. The participant will return for an End of Study/Safety Follow-Up Visit 4 weeks \pm 10 days after the final dose of study-provided medication.
- Participants who have not failed Stage 2 on or before the Stage 2 Week 48 visit will return for an End of Study/Safety Follow-Up Visit 4 weeks \pm 10 days after the final dose of study-provided medication.

Severe lupus manifestations that are life-threatening or organ-threatening should prompt consideration for withdrawal from the study in order to enable maximal therapy with corticosteroids and other lupus medications. The ultimate decision on withdrawal should be left up to the clinical judgment of the investigator.

3.1.3 Stage 3: Re-Randomization

Participants moving into Stage 3 will be re-randomized (1:1) to receive up to 24 weeks of either MMF plus voclosporin (23.7 mg BID) or MMF plus placebo for voclosporin. Individuals who previously received MMF placebo in Stage 2 will receive a 2-week taper-up of MMF (see taper details for Stage 2, Section 3.1.2 *Stage 2: Randomization*). During the first 2 weeks of treatment, a single IM injection of a long-acting corticosteroid may be administered if needed to achieve amelioration of symptoms without meeting the definition of treatment failure in Stage 3 and without a requirement to stop Stage 3 study-provided medication. This single IM corticosteroid injection

[figure not shown]
within the first 2 weeks of Stage 3 treatment may be administered regardless of whether or not one was given at the time of Stage 2 treatment failure for a total of 2 corticosteroid injections (dose will be dependent on the available formulation) with the first injection given as early as the visit where participants have a Stage 2 treatment failure after the mechanistic blood draw and the second injection given as late as the Stage 3 Week 2 Visit. Visits to evaluate AEs, vital signs, hematology and chemistry, study medication compliance, medication use, disease status, participant reported outcomes, and to obtain biomarker samples will occur every 4 weeks after re-randomization.

[figure not shown]
In Stage 3, participants will be on treatment for a maximum of 24 weeks or until treatment failure, whichever occurs first.

- If the participant is deemed a Stage 3 treatment failure, study-provided medication will be stopped. Prior to treatment with a corticosteroid injection or a new or increased lupus medication outside of the study, a blood sample for mechanistic studies will be drawn. The participant will return for an End of Study/Safety Follow-Up Visit 4 weeks \pm 10 days after the final dose of study-provided medication.
- Participants who have not failed Stage 3 on or before the Stage 3 Week 24 visit will return for an End of Study/Safety Follow-Up Visit 4 weeks \pm 10 days after the final dose of study-provided medication.

As in Stage 2, severe lupus manifestations that are life-threatening or organ-threatening should prompt consideration for withdrawal from the study in order to enable maximal therapy with corticosteroids and other lupus medications. The ultimate decision on withdrawal should be left up to the clinical judgment of the investigator.

Figure 1. Study Flow Diagram

3.2 Primary Endpoint

The primary endpoint is the cumulative incidence of participants who experience a Stage 2 treatment failure at or before the Stage 2 Week 24 visit. The criteria for treatment failure are defined in Section 3.5.1, *Treatment Failure*.

3.3 Secondary Endpoints

3.3.1 Efficacy Endpoints

- Clinical response in Stage 2, defined by the BICLA (see Section 3.5.3, *BILAG-based Combined Lupus Assessment (BICLA)*) at Stage 2 Week 24.
- The cumulative incidence of participants who experience a Stage 3 treatment failure, defined as the occurrence of any criteria in Section 3.5.1, *Treatment Failure* after re-randomization and on or before completing Stage 3.
- Time to treatment failure in Stage 3, defined as the interval from the day of Stage 3 randomization until the day of treatment failure.
- Clinical response in Stage 3, defined by the BICLA (see Section 3.5.3, *BILAG-based Combined Lupus Assessment (BICLA)*) at Stage 3 Week 24.

3.3.2 Safety Endpoints

The following specific events will be evaluated separately for each stage of the study:

- The incidence of Grade 3 or higher related AEs.
- The incidence of Grade 3 or higher infections.
- The incidence of renal dysfunction, defined as Grade 3 or higher chronic kidney disease with eGFR < 30 ml/min per 1.73 m².
- The incidence of Grade 3 or higher hypertension, defined as a systolic blood pressure ≥ 160 mm Hg or a diastolic blood pressure of ≥ 100 mm Hg.

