In a combined safety analysis of the three clinical trials (AURORA 1, AURA-LV and AURION) and the ongoing continuation study AURORA 2, the most common AEs were in Infections and Infestations, reported by 66% and 59% of participants respectively [26, 27, 65], in the voclosporin/MMF and placebo/MMF groups. The majority were mild or moderate. Gastrointestinal disorders were also common in both voclosporin/MMF and placebo/MMF groups (49% and 38%, respectively), predominantly diarrhea and nausea. The most common individual AEs in voclosporin-treated participants were glomerular filtration rate (GFR) decreased (voclosporin: 29%, placebo 11%) and hypertension (voclosporin 21%, placebo 11%), both known effects of CNIs. The majority of GFR decreases were of mild to moderate intensity and resolved following temporary interruption or modification of dose per protocol guidance based on theeGFR. SAEs occurred in a similar proportion of participants in the voclosporin/MMF and placebo/MMF groups (28% and 25%, respectively). Infections and infestations were the most common SAEs reported in both groups (12% and 13%, respectively). Serious opportunistic infections were uncommon (<1%) in both treatment groups. Seventeen participants (2.5%) died due to AEs occurring on or within 30 days of the last dose of study treatment (10 (2.7%) voclosporin/MMF, 7

(2.6%) placebo/MMF). None of the AEs leading to death were considered by the investigator, sponsor or the DSMB to be related to study treatment. The reasons for death were consistent with the types of comorbid conditions and complications that would be expected in a population with LN.

2 Study Hypotheses/Objectives

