4.3 Exclusion Criteria

Participants who meet any of the following criteria are not eligible for randomization as study participants:

1. Inability or unwillingness of a participant to understand and provide written informed consent or comply with the study protocol.
2. BILAG A (severe) disease in the Cardiorespiratory, Neuropsychiatric, Gastrointestinal, Ophthalmic, Renal, or Hematological Systems.
3. Severe or unstable nephritis defined as any of the following:
 - a. History of confirmed Class 3-5 nephritis within the last 2 years,

- b. History of confirmed Class 3-5 nephritis > 2 years ago in the absence of documented treatment including both induction and maintenance therapy,
- c. UPCR > 1 g/g at screening,
 - If UPCR is > 0.5 g/g and ≤ 1 g/g at screening, then a second assessment must be completed with at least 1 week between assessments. If the second assessment is > 1 g/g or has increased by ≥ 0.3 g/g, then the participant is excluded.

4. Evidence of chronic kidney disease defined as eGFR < 45 mL/min per 1.73 m² at screening, where $175 \times (\text{Creatinine}/88.4) - 1.154 \times (\text{Age}) - 0.203 \times (0.742 \text{ if female}) \times (1.212 \text{ if of African descent})$ [5].

5. History of cirrhosis or chronic liver disease unrelated to SLE other than fatty liver disease.

6. History, within 1 year of the Screening Visit, of uncontrolled SLE that would have warranted a BILAG A (except mucocutaneous, constitutional, musculoskeletal) including, but not limited to, hemolytic anemia, neuropsychiatric lupus, or interstitial lung disease.

7. Uncontrolled HTN at the Screening or Randomization Visits defined as a blood pressure > 150/100 with or without treatment, not to exceed 3 complementary antihypertensive treatments.

8. Any of the following laboratory values during screening:

- a. Hemoglobin (Hg) < 8.0 g/dL,
- b. WBC < 2.0 × 10⁹ cells/L,
- c. ANC < 1.0 × 10⁹ cells/L,
- d. Platelets < 60 × 10⁹ cells/L at screening,
 - If platelets < 70 × 10⁹ cells/L at screening, platelet count should be retested 2 weeks later. If platelets are < 60 × 10⁹ cells/L at retest, participant will be excluded
- e. AST or ALT > 2.5 times the ULN,
- f. Serum IgG levels < 5 g/L

9. Use of ≥ 40 mg/day of prednisone within 4 weeks prior to the Screening Visit or use of > 20 mg/day of prednisone at screening.

10. Unwilling or unable to taper to ≤ 10 mg/day of prednisone or equivalent by the day of randomization.

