5.2 Risks of voclosporin as cited in the Investigator Brochure and Package Insert

Risks cited below are noted in the voclosporin Investigator's Brochure [65] and Package Insert [21].

Contraindications:

- Voclosporin is contraindicated in patients with hypersensitivity or anaphylactic reactions to voclosporin or any constituents [65].
- Voclosporin should not be given with strong CYP3A4 inhibitors (e.g., ketoconazole, itraconazole, clarithromycin). Voclosporin exposure was 18-fold higher in the presence of the strong CYP3A4 inhibitor (ketoconazole) compared to voclosporin administered alone [65].
- Voclosporin should not be given in patients with hypertensive urgency or BP > 165/105 mmHg [21].
- Voclosporin is not recommended for patients with a baseline eGFR < 45 mL/min per 1.73 m² unless benefit exceeds risks [21].

Hypertension: Voclosporin can cause or worsen systemic HTN. Mild or moderate HTN is encountered more frequently than severe HTN. Serious adverse drug reactions (SADR) classified by the MedDRA preferred term "hypertension" are considered "expected" for the purpose of regulatory reporting. Life-threatening or fatal SADRs are "unexpected". HTN may require antihypertensive therapy.

Decreases in GFR: Voclosporin can cause chronic and/or acute nephrotoxicity. eGFR should be monitored regularly and dose adjustments considered for decreases in eGFR. In the first 4 weeks of treatment with voclosporin, hemodynamic reductions in eGFR have been observed, which subsequently stabilize. Chronic nephrotoxicity has been observed at levels of CNI suppression needed in organ transplantation. The level of CNI suppression of voclosporin in LN is lower than that generally required in transplantation induction and maintenance. Renal impairment and acute kidney injury occurred more frequently in voclosporin-treated patients than placebo-treated patients.

Serious Infections: Immunosuppressants, including voclosporin, may increase the risk of developing bacterial, viral, fungal, and protozoal infections, including opportunistic infections. These infections may be serious and have fatal outcomes. Serious infections are listed as a boxed warning in the package insert [21].

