6.4.7 Decreases in eGFR

For voclosporin use, regular monitoring of eGFR is recommended per the Investigator Brochure, every 2 weeks for first month then every 4 weeks thereafter. Clinically significant decreases have been observed with voclosporin plus

MMF as well as for MMF alone. For this study, individuals with eGFR < 45 mL/min per 1.73 m² at screening are excluded. eGFR will be evaluated at each study visit. It will also be assessed at a Stage 3 Week 2 Safety Check Visit two weeks after initiating Stage 3 therapy. The most recent assessment of eGFR before the Stage 3 Re-randomization Visit should be used as baseline for Stage 3 Week 2 eGFR assessment.

If eGFR < 60 mL/min per 1.73 m² and is reduced from Stage 3 baseline by 20-30%, reduce dose by one capsule BID (total of 2 capsules BID). Reassess eGFR in 2 weeks, and if it is still reduced by > 20% from baseline, reduce dose to 1 capsule BID. If eGFR < 60 mL/min per 1.73 m² and reduced from Stage 3 baseline by > 30%, withhold voclosporin for 2 weeks, then reassess and consider re-initiating at 1 capsule BID if eGFR is > 80% of baseline.

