12.3 Grading and Attribution of Adverse Events

12.3.1 Grading Criteria

The study site will grade the severity of AEs experienced by the study participants according to the criteria set forth in the National Cancer Institute's Common Terminology Criteria for Adverse Events (CTCAE) 5.0 other than exceptions listed below. This document (referred to herein as the NCI-CTCAE manual) provides a common language to describe levels of severity, to analyze and interpret data, and to articulate the clinical significance of all AEs. The NCI-CTCAE has been reviewed by the Protocol Chair and has been deemed appropriate for the participant population to be studied in this protocol.

AEs will be graded on a scale from 1 to 5 according to the following standards in the NCI-CTCAE manual:

- Grade 1 = mild adverse event
- Grade 2 = moderate adverse event
- Grade 3 = medically significant adverse event
- Grade 4 = life-threatening or urgent intervention indicated adverse event
- Grade 5 = death

Events grade 2 or higher and all Grade 1 or higher COVID-19 events will be recorded on the appropriate AE eCRF for this study.

For grading an abnormal value or result of a clinical or laboratory evaluation (including, but not limited to, a radiograph, an ultrasound, an electrocardiogram etc.), an AE is defined as an increase in grade from screening or from the last post-screening value that doesn't meet grading criteria. If a specific event or result from a given clinical or laboratory evaluation is not included in the NCI-CTCAE manual, then an abnormal result would be considered an AE if changes in therapy or monitoring are implemented as a result of the event/result.

Liver function abnormalities will be graded using alternative criteria which are based on CTCAE version 4.0, and are defined relative to the ULN as follows:

- Aspartate aminotransferase [AST] increased
 - Grade 1: > ULN - 3.0x ULN
 - Grade 2: > 3.0x ULN - 5.0x ULN
 - Grade 3: > 5.0x ULN - 20.0x ULN
 - Grade 4: > 20.0x ULN
- Alanine aminotransferase [ALT] increased
 - Grade 1: > ULN - 3.0x ULN
 - Grade 2: > 3.0x ULN - 5.0x ULN
 - Grade 3: > 5.0x ULN - 20.0x ULN
 - Grade 4: > 20.0x ULN

- Alkaline phosphatase [ALP] increased
 - Grade 1: > ULN - 2.5x ULN
 - Grade 2: > 2.5x ULN - 5.0x ULN
 - Grade 3: > 5.0x ULN - 20.0x ULN
 - Grade 4: > 20.0x ULN
- Blood bilirubin increased
 - Grade 1: > ULN - 1.5x ULN
 - Grade 2: > 1.5x ULN - 3.0x ULN
 - Grade 3: > 3.0x ULN - 10.0x ULN
 - Grade 4: > 10.0x ULN

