13.4.4 Analyses of Secondary Safety Endpoints

Safety analyses will be performed on the safety sample and will be assessed by summarizing AEs separately for each stage of the study. The length of time participants are followed within each stage is variable and could depend on if a participant meets treatment failure. To account for potential differential duration of study participation, AE summaries by treatment group will include the number of events per person-year in addition to the number and percentage of events and participants experiencing events. AEs and SAEs will be summarized by system organ class, preferred term, and severity grade.

Safety endpoints identified in Section 3.3.2 Safety Endpoints, will be summarized and listed separately for each stage of the study. For each such endpoint, the number of events per person-year as well as numbers and percentages of events and participants who experience these events will be summarized overall in Stage 1 and by treatment group in Stage 2 and 3. No formal statistical testing will be performed to compare safety between treatment groups.

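### The only renal-specific safety endpoint (eGFR < 30) will rarely register the GFR decrease expected with voclosporin, and no analysis of eGFR change in Stage 3 is planned

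*Combined protocol and SAP*

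**What the plan says.** Section 3.3.2 lists four safety endpoints, evaluated by stage. The only renal-specific one is renal dysfunction, "defined as Grade 3 or higher chronic kidney disease with eGFR < 30 ml/min" per 1.73 m². A second, "The incidence of Grade 3 or higher related AEs", would also include a related renal event of that grade.

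Section 1.5.2.3 describes the most common individual AEs on voclosporin in the pooled nephritis trials: GFR "decreased (voclosporin: 29%, placebo 11%) and hypertension (voclosporin 21%, placebo 11%), both known effects of CNIs". It adds that most GFR decreases were mild to moderate and resolved after dose interruption or modification. Section 5.2 reports early eGFR reductions in the first 4 weeks that later stabilise.

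Section 6.4.7 schedules eGFR at each study visit and at a Stage 3 Week 2 safety check. It manages eGFR as a percentage fall: one step applies if eGFR is under 60 and "is reduced from Stage 3 baseline by 20-30%, reduce dose by one capsule BID", and a further step applies to falls above 30%.

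For analysis, Section 13.4.4 states: "Safety endpoints identified in Section 3.3.2 Safety Endpoints, will be summarized and listed separately for each stage of the study". It also tabulates AEs by treatment group, system organ class, preferred term and grade, with events per person-year and no formal testing. Section 12.3.1 records AEs of Grade 2 or higher (Grade 1 or higher for COVID-19). For laboratory values, "an AE is defined as an increase in grade from screening or from the last post-screening value that doesn't meet grading criteria". Section 13.4.7 adds baseline data, disposition, medication use and AEs.

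**The concern.** The protocol anticipates a specific renal effect, measures it often and manages it as a percentage fall from the Stage 3 baseline. The planned analysis does not use that scale. The one named renal endpoint is a fixed low eGFR, which most mild or moderate falls will not reach.

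Describing the safety of MMF plus voclosporin is a secondary objective (Section 2.3), and Section 5.6 says voclosporin has not been evaluated in SLE without nephritis. A renal dysfunction row with few or no events in either arm could be read as reassurance when the endpoint was simply insensitive to the expected effect.

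There is also a link to efficacy. Section 6.5 allows study therapy to be discontinued for an eGFR decrease that does not resolve, and Section 3.5.1 counts permanent discontinuation for any reason as treatment failure. Without a by-arm count of renal discontinuations, renal toxicity could enter the Stage 3 failure result without being visible as such.

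**Working it through.** The plan gives no sample size, power or expected count for the renal endpoint, so there is no figure of its own to reproduce.

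**Inputs.** Endpoint threshold 30 (3.3.2). Screening limit 45 (4.3: "Evidence of chronic kidney disease defined as eGFR < 45 mL/min per 1.73 m² at screening"). Cut-points of 20% and 30% (6.4.7). AE rates of 29% and 11% (1.5.2.3). Stage 3 size from 13.7.

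**Fall needed to reach the endpoint:** 1 − 30/baseline. The last two columns are baseline × (1 − fall).

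| Baseline eGFR | Fall must exceed | After a 20% fall | After a 30% fall |
|---|---|---|---|
| 45 | 33.3% | 36.0 | 31.5 |
| 60 | 50.0% | 48.0 | 42.0 |
| 90 | 66.7% | 72.0 | 63.0 |

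**Baseline from which a given fall goes below 30:** 30/(1 − fall).
- 20% fall: baseline under 37.5
- 30% fall: baseline under 42.9
- 40% fall: baseline under 50.0

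So a fall of 20% or 30% from 45 or above does not count. A larger fall can: 35% from 45 gives 45 × 0.65 = 29.25.

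**A large fall outside both rules.** From 110 to 65 the fall is 1 − 65/110 = 40.9%. It misses the endpoint because 65 is above 30, and it misses the Section 6.4.7 steps because they require eGFR under 60.

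**Stage 3 size.** 0.80 × 60 = 48 from placebo and 0.60 × 60 = 36 from MMF. Re-randomised 1:1, that is 24 + 18 = 42 per arm.

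**Expected participants with a GFR-decrease AE, if the nephritis-trial rates applied.** 42 × 0.29 = 12.2 on voclosporin and 42 × 0.11 = 4.6 on placebo, about 12 vs 5.

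**Reference values compared.** Section 6.4.7 uses the Stage 3 baseline, the most recent value before re-randomisation. Section 12.3.1 uses either the screening grade or the last later value that did not meet grading criteria. The second may coincide with the Stage 3 baseline in some participants but is not defined as it. A grade also does not show the percentage fall or its time course.

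**The case against.** The strongest reply is that the AE tables already do this job. They are by stage, arm, preferred term and grade, and Grade 2 events are recorded. The 29% and 11% are themselves AE rates. If they held with 42 per arm, the voclosporin arm would show more cases with probability about 0.98 (exact binomial). This largely stands. A reader might infer that Stage 3 could report no renal signal at all, and the documents do not support that. What remains is narrower: AE tables give graded events, not the size, timing or reversal of the fall from the Stage 3 baseline. How many falls would go unrecorded depends on CTCAE cut-offs that the protocol does not give in full.

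Three other stronger readings also fail.
- **A known voclosporin fall of 20-30%.** That range is a dose-modification band, with a tier above 30% beside it. The documents give the incidence of GFR decrease, not its size.
- **An endpoint that cannot be reached.** The limit of 45 applies at screening, and the Stage 3 baseline is a later value that may be lower. Nor does the management rule always act well before 30: from 45, its 30% cut-point lies at 31.5. It also acts only after a measurement, and a first value below 30 already counts.
- **The same weakness in blood pressure.** Section 5.2 does say "Mild or moderate HTN is encountered more frequently than severe HTN". But exclusion 7 is a pressure above 150/100 and the endpoint counts diastolic ≥ 100 or systolic ≥ 160. A participant can enter at diastolic 100, which already meets it, or at systolic 150, needing a rise of 10. That endpoint is readily reachable.

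It is also fair to say that the four listed endpoints are mainly for severe events, that Stage 3 is exploratory and that no safety test is planned. This limits the weight of the point, but a descriptive objective still needs a measure that can describe the expected effect.

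**Conclusion.** The point holds as a gap in the descriptive safety plan. The eGFR < 30 endpoint is legitimate for severe loss of renal function but insensitive to the mostly mild-to-moderate decrease the protocol expects: more than a third of eGFR must be lost even from the screening limit, and more than half from 60. No planned analysis uses the percentage scale of Section 6.4.7.

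The 12 vs 5 illustration assumes that rates from lupus nephritis trials carry over. Those trials ran 48 or 52 weeks, with a continuation of up to 24 months. Stage 3 lasts at most 24 weeks and excludes severe or unstable nephritis, so the true counts could differ. That the endpoint will rarely be met is a judgement from the threshold arithmetic; the documents give neither a baseline eGFR distribution nor an effect size from which to compute a probability. The primary analysis is unaffected.

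**What to change.** Keep the eGFR < 30 endpoint. In Sections 3.3.2 and 13.4.4, add these descriptive Stage 3 summaries by arm:

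- (a) percent change in eGFR from the Stage 3 baseline at Week 2, Week 4, each later visit and Safety Follow-Up, with the number of participants contributing at each;
- (b) the proportion with a fall of at least 20%, and of more than 30%, at any visit, whatever the absolute eGFR, using the cut-points already in Section 6.4.7;
- (c) the proportion with a voclosporin/placebo dose reduction, hold or discontinuation for eGFR.

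State that the Stage 3 baseline is the last eGFR before re-randomisation for all these summaries; Section 6.4.7 defines it explicitly only for the Week 2 assessment. Because follow-up ends at treatment failure, report person-time with (b) and (c), as Section 13.4.4 already does for AEs. A by-arm summary of blood-pressure change is optional.

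The cost is protocol and SAP wording and a few tables. The eGFR measurements are already scheduled. For (c), confirm that the eCRF records the reason for each dose change, which the protocol does not state. No dose or management rule changes.
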